7.2.3.5. PR with Lymphocytosis (PRL)

Subjects achieve all PR criteria with the exception of lymphocyte criteria.

7.2.3.6. Stable Disease (SD)

Not meeting criteria for CR, CRi, nPR, PR, PRL, or progressive disease.

7.2.3.7. Progressive Disease (PD)

A CT scan is required to evaluate all cases of suspected progressive disease for this protocol regardless of the modality of disease progression (eg, lymph node, lymphocytosis, or transformation). Progressive disease requires at least ONE of following:

- New enlarged nodes >1.5cm, new hepatomegaly or splenomegaly; or other organ infiltrates
- $\geq 50\%$ increase from nadir in existing lymph node (must reach >1.5 cm in the longest diameter) or $\geq 50\%$ increase from nadir in sum of product of diameters of multiple nodes
- $\geq 50\%$ increase from nadir in enlargement of liver or spleen
- $\geq 50\%$ increase from the baseline ALC count and at least $5 \times 10^9/L$
- New cytopenia (hemoglobin or platelets) attributable to CLL. The progression of any cytopenia (unrelated to autoimmune cytopenia, drugs, or bleeding), as documented by a decrease of Hgb levels from baseline by more than 20 g/L (2 g/dL) or to less than 100 g/L (10 g/dL) and lower than baseline, or by a decrease of platelet counts from baseline by $\geq 50\%$ or to less than $100 \times 10^9/L$ (100,000/ μL) and lower than baseline in the presence of active CLL, defines disease progression ; a marrow biopsy must demonstrate an infiltrate of clonal CLL cells if no other evidence of disease progression is present on CT scan.
- Transformation to a more aggressive histology (eg, Richter's Transformation). Whenever possible, this diagnosis should be established by biopsy.

Suspected progressive disease (eg, by PE or ALC) must be confirmed by a serial exam at least 2 weeks later, and confirmed by imaging.

7.2.4. Hematological Improvement

Hemoglobin and platelet counts will be evaluated.

7.2.5. Radiographic Images Assessment

Radiological efficacy assessments, for the purpose of the study result analyses, will be performed by the Investigator. For the MRD and Fixed Duration cohorts, imaging will be collected and stored centrally. The Sponsor may utilize IRC for independent review of efficacy with details to be outlined in the separate IRC charter.

The baseline disease assessment will include all areas of known and suspected disease with use of the most appropriate and reproducible radiological technique.

Radiological imaging by CT with contrast is required and must include the neck, chest, abdomen, and pelvis. Subjects who are intolerant to IV CT contrast agents will have CT scans performed with oral contrast. When possible, all subjects should have radiographic tumor measurements performed at the participating study center or an acceptable alternate imaging facility using an identical imaging protocol and similar equipment. The same imaging equipment should be utilized for all scans whenever possible. The same radiologist should be assigned to read all the scans for a given subject throughout the study as much as possible.

Magnetic resonance imaging (MRI) may be used to evaluate non-target lesions that cannot be adequately imaged using CT (in cases where MRI is desirable, the MRI must be obtained at baseline and at all subsequent response evaluations). If MRI is required for any other reason, this must be discussed with the study Medical Monitor first.

CT scans will be performed until disease progression regardless of whether or not the subject remains on treatment. In the event disease progression is suspected due to physical examination or laboratory test, a CT scan must be performed to confirm disease progression.

There must be radiographically measurable disease at Screening (at least one lymph node >1.5 cm in the longest diameter) as outlined in [Section 7.2.2](#). If the sole lesion lies within the field of prior radiotherapy, there must be evidence of disease progression in that lesion.

Up to 6 measurable lymph nodes (target lesions >1.5 cm in the longest diameter), clearly measurable in 2 perpendicular dimensions, will be followed as target lesions for each subject. Measurable sites of disease should be chosen such that they are representative of the subject's disease. In addition, selection of target lesions should be from as disparate regions of the body as possible when these areas are significantly involved. If additional lesions are present but are not included in the target lesion assessment, they can be added as non-target lesions followed throughout the study.

The cranial-caudal measurement of the spleen and longest diameter of the liver will be assessed at Screening and all subsequent response evaluations.

7.3. Suspected Disease Progression

The schedule of assessments is provided in [Appendix A](#) and [Appendix B](#). Any suspected case of disease progression will prompt procedures performed in a Suspected Disease Progression visit ([Section 8.5](#)). Disease progression should be confirmed with a CT scan (or MRI, if CT is contraindicated) and should be reported to the Sponsor within 24 hours of discovery. If disease progression is suspected based on the results of a single examination or a single laboratory parameter, this finding should be confirmed by a subsequent evaluation at least 2 weeks later and confirmed by imaging.

Study treatment should be continued and new anti-cancer therapy withheld, if clinically appropriate, until disease progression is confirmed by the Investigator. Subjects should continue to adhere to all study-related procedures—including response evaluations and procedures to confirm disease progression—until clinical progressive disease is confirmed by the Investigator. When disease progression has been confirmed by the Investigator, study treatment should be discontinued.

If there is uncertainty regarding whether there is disease progression, the subject should continue study treatment and remain under close observation (eg, evaluated at 2-4 week intervals). Transient worsening of disease during temporary interruption of study therapy (eg, for drug-related toxicity, intercurrent illness, or surgery) may not indicate disease progression.

7.4. Sample Collection and Handling

The actual dates and times of sample collection must be recorded in source documents for transcription to the eCRF or laboratory requisition form. Refer to the Schedule of Assessments ([Appendix A](#), [Appendix B](#), [Appendix C](#), [Appendix D](#), and [Appendix E](#)) for the timing and frequency of all sample collections.

Instructions for the collection, handling, and shipment of samples are found in the Laboratory Manual.

8. STUDY PROCEDURES

8.1. Screening Period

Screening procedures will be performed up to 30 days prior to initiation of study drug, unless otherwise specified. All subjects must first read, understand, and sign the IRB/REB/IEC-approved ICF before any study-specific screening procedures are performed. All study tests and procedures should be performed at the study center at which the subject was enrolled and will be receiving treatment. After signing the ICF, and being deemed eligible for entry, subjects may be enrolled in the study.

8.1.1. Screening Visit

The following procedures will be performed at the Screening Visit within 30 days prior to enrollment unless otherwise noted:

- Obtain signed, written informed consent
- Medical history including demographic information
- Perform a complete physical examination, including height and weight (may use prior height measurement if available in source documents)
- Evaluation of ECOG performance status

- Obtain vital signs (including blood pressure, heart rate, and body temperature) after the subject has rested in the sitting position for at least 3 minutes
- Obtain triplicate 12 lead ECG (≥ 1 minute apart) after the subject has been in a supine position and resting for at least 10 minutes.
- Record concomitant medication history including over-the-counter drugs, vitamins and herbs
- Adverse events (record as Medical History on eCRF form)
- Imaging by CT or other modality as described in [Section 7.1.3.2](#) (if not performed within 6 weeks prior to enrollment)
- Obtain a bone marrow aspirate and biopsy (if not performed within 90 days prior to enrollment) (local and central labs [MRD Cohort]; local labs [FD Cohort])
- Obtain blood specimens for the following laboratory tests:
 - Hematology
 - Serum chemistry (including creatinine clearance)
 - Coagulation panel (PT/INR, aPTT)
 - Hepatitis serologies
 - Obtain serum pregnancy test for women of childbearing potential only

8.2. MRD Cohort

For the MRD cohort, the study is divided into a Screening Phase, a Pre-randomization Treatment Phase, a Randomization Phase, and a Post-PD Follow-up Phase. The Schedule of Assessments ([Appendix A](#)) summarizes the frequency and timing of efficacy, PK, [REDACTED] and safety measurements applicable to this study. The timing of all visits will be based on using Cycle 1 Day 1 (C1D1) as the anchor visit and all subsequent visits should use the C1D1 date as the basis for scheduling.

MRD Cohort: Pre-Randomization Treatment Phase

Refer to the Schedule of Assessments ([Appendix A](#)) for a complete list of procedures to be performed at each scheduled study visit.

Following completion of the Screening Visit and once eligibility has been confirmed (per inclusion/exclusion criteria), subjects will initiate ibrutinib treatment. Venetoclax will be added to ibrutinib treatment and initiated after completion of 3 cycles of ibrutinib. The venetoclax dose will be ramped up over 5 weeks per standing dosing recommendations (see [Section 5.3.1](#) for ibrutinib and venetoclax dosing).

Subjects who are unable to complete at least 12 cycles of combination therapy will not be eligible for Randomization but will continue to follow the same visit schedule until disease

progression. After disease progression subjects will enter the Post-PD Follow up Phase (Section 8.8).

8.2.1. Treatment Visits

8.2.1.1. Cycle 1 Day 1 (C1D1) Visit

Pre-Dose

The following procedures will be performed prior to dosing (within 3 days) of the C1D1 Visit. Please note, C1D1 Visit procedures done at Screening will not need to be repeated **if done within 3 days of first dose with study drug.**

- Confirm eligibility (per inclusion/exclusion criteria) and enroll subject. Dosing should occur within 3 days of confirmation.
- Adverse events
- Physical examination
- Vital signs
- ECOG performance status
- Concomitant medications
- Hematology
- Serum chemistry (including creatinine clearance)
- Tumor Lysis Risk assessment (use Screening CT and C1D1 ALC. see [Appendix H](#) for risk assessment categories)
- XXXXXXXXXX
- IGHV (if IGHV sample is not informative for any reason, another peripheral blood sample should be drawn and sent to the central lab at the next appropriate timepoint)
- FISH panel
- Karyotype
- Buccal Swab
- MRD in peripheral blood
- Perform urine pregnancy test for women of childbearing potential only

Dosing and Post First Dose

- In-clinic administration of ibrutinib
- Dispense ibrutinib for offsite use and provide study drug compliance instructions

8.2.1.2. Cycles 2 and 3 Visits

Pre-Dose

The following procedures will be performed on Day 1 (± 3 days) of each cycle (except for CT/MRI):

- Adverse events
- Concomitant medications
- Study drug compliance review
- Physical exam
- Vital signs
- ECOG
- CT/MRI (to assess response and lymph node sum of the product of the diameters [SPD] for TLS risk assessment, Cycle 3 only – to be obtained as close to the beginning of Cycle 4 as possible, while still allowing for appropriate TLS risk-guided interventions including hospitalization if appropriate)
- Hematology
- Serum chemistry
- 
- Pharmacokinetics sample (Cycle 2 only. See [Section 7.1.4.1](#) for Pharmacokinetics Sample Collection Schedule)

Dosing and Post Dose

- In-clinic administration of ibrutinib (Cycle 2 only)
- Collection of post dose pharmacokinetics samples per [Section 7.1.4.1](#) (Cycle 2 only)
- Dispense ibrutinib for offsite use and provide study drug compliance instructions

8.2.1.3. Cycle 4 Visits

8.2.1.3.1. Pre-Cycle 4 (Pre-initiation of Venetoclax)

The following procedures will be performed 2-3 days (± 3 days) prior to Cycle 4:

- Overall response assessment
- Hematology
- Serum Chemistry
- Tumor Lysis Risk assessment (see [Appendix H](#) for risk assessment categories)
- Tumor Lysis Syndrome prophylaxis (see [Section 5.4.2.2](#) for prophylaxis schedule based on risk)

The following procedures will be performed 1 day prior to Cycle 4:

- Tumor Lysis Syndrome prophylaxis (see [Section 5.4.2.2](#) for prophylaxis schedule based on risk)

8.2.1.3.2. Cycle 4 Week 1 Day 1

Pre-Dose

The following procedures will be performed on Day 1 (± 3 days) of Cycle 4, Week 1:

- Adverse events
- Concomitant medications
- Study drug compliance review
- Physical exam
- Vital signs
- ECOG
- Hematology
- Serum chemistry
- Creatinine clearance (Cockcroft-Gault)
- Tumor Lysis Risk assessment (see [Appendix H](#) for risk assessment categories)
- Tumor Lysis Syndrome prophylaxis (see [Section 5.4.2.2](#) for prophylaxis schedule based on risk, venetoclax administration setting, and frequency of serum chemistry monitoring assessments)
- ██████████ assays

Dosing and Post First Dose of Venetoclax

- In-clinic administration of ibrutinib
- In-clinic administration of venetoclax 20 mg for low and medium risk TLS subjects
- Consider hospitalization for first dose of venetoclax 20 mg in medium risk TLS subjects with a CrCl < 80 mL/min
- In-hospital administration of first dose of venetoclax 20 mg for high risk TLS subjects
- Dispense ibrutinib and venetoclax for offsite use and provide study drug compliance instructions

8.2.1.3.3. Cycle 4 Week 1 Day 2

Pre-Dose

- Adverse events
- Hematology
- Serum chemistry

- Tumor Lysis Syndrome prophylaxis (see [Section 5.4.2.2](#) for prophylaxis schedule based on risk and frequency of serum chemistry monitoring assessments)

8.2.1.3.4. Cycle 4 (Week 2 – Week 4) Visits

The following procedures will be performed on Day 1 (± 3 days) of Cycle 4, Weeks 2, 3, and 4 (coincides with venetoclax standard dose ramp-up of 50 mg (W2D1), 100 mg (W3D1), and 200 mg (W4D1))

Pre-Dose

- Adverse events
- Concomitant medications
- Study drug compliance review
- Physical exam
- Vital signs
- ECOG
- Hematology
- Serum chemistry
- Creatinine clearance (Cockcroft-Gault)
- Tumor Lysis Syndrome Risk assessment (see [Appendix H](#) for risk assessment categories)
- Tumor Lysis Syndrome prophylaxis (see [Section 5.4.2.2](#) for prophylaxis schedule based on risk and frequency of serum chemistry monitoring assessments)

Dosing and Post-Dose

- In-clinic administration of venetoclax 50 mg (Week 2), 100 mg (Week 3) and 200 mg (Week 4) for low and medium TLS risk subjects
- Consider hospitalization for first dose of venetoclax 50 mg in medium risk TLS subjects with a CrCl < 80 mL/min
- In-hospital administration of first dose of venetoclax 50 mg dose at week 2 for high risk TLS subjects; in-clinic administration of venetoclax 100 mg (Week 3) and 200 mg (Week 4) for high risk TLS subjects
- Dispense venetoclax for offsite use and provide study drug compliance instructions

8.2.1.3.5. Cycle 4 Week 2 Day 2

Pre-Dose

- Adverse events
- Hematology
- Serum chemistry

- Tumor Lysis Syndrome prophylaxis (see [Section 5.4.2.2](#) for prophylaxis schedule based on risk and frequency of serum chemistry monitoring assessments)

8.2.1.4. Cycle 5 Visits

8.2.1.4.1. Cycle 5 Week 1 and Week 3 Visits

Pre-Dose

The following procedures will be performed on Day 1 (± 3 days) of Cycle 5, Week 1 and Week 3:

- Adverse events
- Concomitant medications
- Study drug compliance review
- Physical exam
- Vital signs
- ECOG
- Hematology
- Serum chemistry
- Creatinine clearance (Cockcroft-Gault)
- Tumor Lysis Syndrome Risk assessment (see [Appendix H](#) for risk assessment categories) (Week 1 Only)
- Tumor Lysis Syndrome prophylaxis (see [Section 5.4.2.2](#) for prophylaxis schedule based on risk, venetoclax administration setting, and frequency of serum chemistry monitoring assessments) (Week 1 Only)

Dosing and Post-Dose

- In-clinic administration of venetoclax
- Dispense ibrutinib and venetoclax for offsite use and provide study drug compliance instructions (Week 1 only)

8.2.1.5. Cycle 6 – Cycle 9 Visits

Pre-Dose

The following procedures will be performed on Day 1 (± 3 days) of Cycles 6, 7, 8, and 9:

- Adverse events
- Concomitant medication
- Study drug compliance review

- Physical exam
- Vital signs
- ECOG
- Hematology
- Serum chemistry
- Overall response assessment (by PE/CBC Cycle 7 only)
- MRD in peripheral blood (Cycle 7 only)
- ██████████ assays ██████████
- Pharmacokinetics sample (Cycle 6 only. See [Section 7.1.4.1](#) for Pharmacokinetics Sample Collection Schedule)

Dosing and Post-Dose

- In-clinic administration of ibrutinib (Cycle 6 only)
- In-clinic administration of venetoclax (Cycle 6 only)
- Collection of post dose pharmacokinetics samples per [Section 7.1.4.1](#) (Cycle 6 only)
- Dispense ibrutinib and venetoclax for offsite use and provide study drug compliance instructions

8.2.1.6. Cycle 10 & Cycle 13 Visits

Pre-Dose

The following procedures will be performed on Day 1 (± 3 days) of Cycles 10 and 13:

- Adverse events
- Concomitant medications
- Study drug compliance review
- Physical exam
- Vital signs
- ECOG
- Hematology
- Serum chemistry
- CT/MRI (Cycle 10 only)
- Overall response assessment
- MRD assessment (in peripheral blood)
- ██████████ assays

Post-Dose

- Dispense ibrutinib and venetoclax for offsite use and provide study drug compliance instructions

8.2.1.7. Cycle 16 Day 1 Visit**Pre-Dose**

The following procedures will be performed on Day 1 (± 3 days) of Cycle 16:

- Adverse events
- Concomitant medications
- Study drug compliance review
- Physical exam
- Vital signs
- ECOG
- Hematology
- Serum chemistry
- CT/MRI
- Overall response assessment
- Bone marrow biopsy (unless collected prior for CR assessment, and confirmed MRD-negative in BM)
- MRD assessment (bone marrow aspirate and peripheral blood). Bone marrow aspirate can be drawn ± 14 days from C16D1.
- ██████████ assays

Post-Dose

- Dispense ibrutinib and venetoclax for offsite use and provide study drug compliance instructions

MRD Cohort: Randomization Phase

Refer to the Schedule of Assessments ([Appendix A](#)) for a complete list of procedures to be performed at each scheduled study visit.

At Cycle 17 (following 3 cycles of ibrutinib lead-in, completion of 12 cycles of ibrutinib + venetoclax combination treatment, plus 1 cycle to evaluate MRD status) or within 3 days before Cycle 17 Day 1 visit, subjects will be randomized based on their MRD status. Randomization will occur via Interactive Response Technology (IRT) or alternative system provided by the Sponsor.

MRD-neg subjects will be randomized to either **ibrutinib or placebo**, and therapy should be continued until MRD-positive relapse, disease progression, unacceptable treatment-related toxicity, or other reasons outlined in [Section 9.2](#).

Subjects not obtaining confirmed MRD-neg responses (considered MRD-pos) will be randomized to either **ibrutinib + venetoclax or ibrutinib alone**. Ibrutinib and/or venetoclax should be continued until disease progression, unacceptable treatment-related toxicity, or other reasons outlined in [Section 9.2](#).

Central labs for MRD assessment will be used to inform randomization strata, and re-introduction of therapy. Local labs will be used to guide all other dosing-related decisions. In the event of rising MRD assessments, or of clinically suspected disease progression, the subject should continue to receive study medication, at the discretion of the Investigator, until MRD-positive relapse or disease progression is confirmed respectively.

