	
OR
 
Placebo
 
 Orally once daily matching placebo capsules (3 capsules) continuously until confirmed MRD-positive relapse, disease progression or unacceptable toxicity 
Randomization Phase – MRD-positive subjects:
 
Ibrutinib + venetoclax
 
 Orally once daily ibrutinib 420 mg (3 capsules) continuously until disease progression or unacceptable toxicity 
plus
 
 Orally once daily venetoclax 400 mg daily (four 100 mg tablets) 
OR
 
Ibrutinib
 
 Orally once daily ibrutinib 420 mg (3 capsules) continuously until disease progression (post reintroduction when applicable) or unacceptable toxicity 
Reintroduction of ibrutinib or venetoclax:
 
Upon confirmed MRD-positive relapse in MRD-negative randomized subjects or confirmed disease progression by IWCLL criteria in any randomized subjects, ibrutinib and/or venetoclax may be reintroduced.
 
Subjects who are receiving placebo treatment, when MRD-positive relapse or disease progression are confirmed, may reintroduce oral daily ibrutinib until disease progression or unacceptable toxicity.
 
Subjects who are receiving oral daily ibrutinib may reintroduce oral daily venetoclax. Standard TLS risk assessment, venetoclax dose ramp up, and TLS management should be employed at venetoclax reintroduction (VENCLEXTA® (venetoclax) prescribing information).
 
2) Fixed Duration Cohort
 
Ibrutinib:
 
 Orally once daily ibrutinib 420 mg (3 capsules) Single-agent lead-in for 3-cycles, then continued in combination for 12 additional cycles until completion of Cycle 15 Dose modification for adverse events are specified in Section 5.4.1.4 
Venetoclax:
 
 Orally once daily venetoclax, with 5-week dose ramp up (VENCLEXTA® (venetoclax) prescribing information), to 400 mg daily, added to ongoing ibrutinib therapy starting at Cycle 4 and continuously for 12 cycles until completion of Cycle 15 Venetoclax and ibrutinib should be dosed together at the same time each day with a meal and water
--	--

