5.3.2.1. Randomization Phase – MRD-negative Subjects (Double-blind)

In the Randomization Phase, subjects who are MRD-negative will be randomized in a blinded fashion to ibrutinib or placebo.

Ibrutinib

- Orally once daily ibrutinib 420 mg (3 capsules) continuously until disease progression (post reintroduction when applicable) or unacceptable toxicity

OR**Placebo**

- Orally once daily matching placebo capsules (3 capsules) continuously until confirmed MRD-positive relapse, disease progression, or unacceptable toxicity

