5.5. Criteria for Permanent Discontinuation of Study Drug

Investigators are encouraged to keep a subject who is experiencing clinical benefit in the study unless significant toxicity puts the subject at risk or routine noncompliance puts the study outcomes at risk. If a subject discontinues one study drug for reasons other than disease progression, the other study drug should be continued per protocol. Refer to Study Design details in [Section 3.1.1](#) and [Section 3.1.2](#). For a complete list of criteria for permanent discontinuation of study treatment, refer to [Section 9.2](#).

An End-of-Treatment Visit ([Section 8.7](#)) is required for all subjects except for those subjects who have withdrawn full consent.

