8.2.2. Cycle 17 Randomization Visit and Every 3 Cycles Thereafter

The following procedures will be performed on Day 1 (± 3 days) of Cycles 17 and every 3 cycles thereafter (unless indicated otherwise) until disease progression, unacceptable treatment-related toxicity, or other reasons outlined in [Section 9.2](#):

Pre-Dose

- Adverse events
- Concomitant medications
- Study drug compliance review
- Physical exam
- Vital signs
- ECOG
- Hematology
- Serum chemistry
- CT/MRI (Cycle 23, Cycle 29, Cycle 35, and then annually thereafter)
- Overall response assessment
- Bone marrow biopsy (± 14 days from C29 unless collected prior for CR assessment, and confirmed MRD-negative in BM)
- MRD assessment (by PB starting Cycle 20, 23, 26, 29, and every 6 cycles thereafter; by bone marrow aspirate [BMA] at Cycle 29 in randomized subjects, and in any subject with MRD-neg conversion in PB; BMA can be drawn ± 14 days from C29D1.)
- ██████████ assays ██████████

Post-Dose

- Dispense randomization specific study medication to subject for off-site use and provide study drug compliance instructions

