9.2. Withdrawal from Study Treatment

Study treatment will be discontinued in the event of any of the following events:

- Confirmed progressive disease
- Unacceptable toxicity: an intercurrent illness or AE that prevents further study drug administration
- Withdrawal of consent for treatment by subject
- Investigator decision (such as chronic noncompliance, significant protocol deviation, or best interest of the subject)
- Study termination by Sponsor
- Subject becomes pregnant
- Death

Subjects in the Randomization Phase of the MRD cohort or subjects in the Fixed Duration cohort who elect to not reintroduce therapy after confirmed PD, or have a confirmed PD after reintroduction of therapy, will be withdrawn from study treatment.

All subjects, regardless of reason for discontinuation of study treatment will undergo an End -of -Treatment Visit and be followed for progression and survival.

The investigator should notify the Sponsor within 24 hours if a subject discontinues ibrutinib and/or venetoclax treatment due to disease progression and should provide documentation of disease progression for review by the Sponsor's Medical Monitor. If a subject shows signs of disease progression on physical examination or laboratory assessment, the subject may continue study treatment until disease progression is confirmed. These subjects should stay in the study to be followed for survival.

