### 1.1. Study Design

This is an international multicenter, 2-cohort Phase 2 study assessing both minimal residual disease (MRD)-guided discontinuation and fixed duration (FD) therapy with the combination of ibrutinib + venetoclax (‘Ibr + Ven’ hereafter) in subjects with treatment-naïve chronic lymphocytic leukemia (CLL) or small lymphocytic lymphoma (SLL). Figure 1 outlines the study design.

The MRD cohort begins with the same 15-cycle treatment (3 cycles of ibrutinib single agent lead-in followed by 12 cycles of Ibr + Ven) as in the FD cohort. This is followed by 1 cycle of Ibr + Ven during which MRD-guided randomization occurs, after which treatment proceeds according to the randomization. MRD negativity is assessed by a central laboratory and defined as  $<1$  CLL cell per 10,000 leukocytes ( $<1 \times 10^{-4}$ ), as assessed by flow cytometry of a peripheral blood (PB) or bone marrow (BM) aspirate sample. MRD negativity for randomization purposes must be confirmed serially over at least 3 cycles and must be negative in both bone marrow and peripheral blood.

The randomized treatment for MRD cohort starts from cycle 17 day 1. MRD-negative randomized subjects are randomized to receive double blind ibrutinib or placebo and to be treated until MRD relapse or disease progression (PD) or unacceptable toxicity. MRD-positive randomized subjects are randomized to receive open label ibrutinib or ibrutinib + venetoclax: ibrutinib is to be continued until PD or unacceptable toxicity in either arm, while venetoclax can be administered for up to 2 years cumulatively (including pre-randomization and randomization phases) or until PD or unacceptable toxicity, whichever the earliest.

The FD cohort is an open-label, 1 arm cohort with a fixed duration 15-cycle treatment: 3 cycles of ibrutinib single agent lead-in followed by 12 cycles of Ibr + Ven. This cohort was added in Protocol Amendment 1 after the completion of MRD cohort enrollment. Each cycle consists of 28 days.

All subjects who discontinue treatment in the absence of disease progression will remain on response follow-up until confirmed PD or until study closure. After PD, subjects will be followed for survival and subsequent anti-cancer therapies. Treatment reintroduction is allowed per investigator’s discretion for both cohorts as following:

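### Protocol 8.2 and SAP 1.1 stop both double-blind arms at MRD-positive relapse, while Protocol 5.3.2.1 and the synopsis stop only placebo; a site that stays blinded could withdraw active ibrutinib

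*Protocol*

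**What the plan says.** Three versions of the stopping rule for the double-blind arms stand in the documents.

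**One rule for both arms.** Protocol 8.2 (MRD Cohort: Randomization Phase, after the Cycle 16 visit) says of ibrutinib and placebo together that "therapy should be continued until MRD-positive relapse, disease progression, unacceptable treatment-related toxicity" or another reason in 9.2. SAP 1.1 agrees: "MRD-negative randomized subjects are randomized to receive double blind ibrutinib or placebo and to be treated until MRD relapse or disease progression", or unacceptable toxicity.

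**An arm-specific rule.** Protocol 5.3.2.1 gives ibrutinib as "Orally once daily ibrutinib 420 mg (3 capsules) continuously until disease progression (post reintroduction when applicable) or unacceptable toxicity", and the synopsis agrees. For placebo the synopsis has "Orally once daily matching placebo capsules (3 capsules) continuously until confirmed MRD-positive relapse, disease progression or unacceptable toxicity", and 5.3.2.1 matches it.

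**MRD-positive relapse named for neither arm.** Section 5.5 says "For a complete list of criteria for permanent discontinuation of study treatment, refer to" Section 9.2. That section opens "Study treatment will be discontinued in the event of any of the following events" and lists progression, toxicity, withdrawn consent, investigator decision, sponsor termination, pregnancy and death. Section 8.2.2 schedules visits and dispensing of randomized medication "until disease progression, unacceptable treatment-related toxicity, or other reasons outlined in" Section 9.2.

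**Unblinding.** SAP 1.7.1 keeps the subject, the investigator and the sponsor's study staff blinded until there is a confirmed relapse or progression and a plan to reintroduce. The code may then be requested, subject to an independent clinician's check of the DFS event and approval in the interactive response system (IRT). The synopsis and Protocol 3.1.2 permit unblinding at confirmed MRD-positive relapse and do not make a plan to reintroduce a condition.

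**The concern.** An arm-specific rule cannot be applied without the treatment code. If the code is available only when reintroduction is planned, a site with a confirmed MRD-positive relapse and no such plan has only the instructions it can follow blind. One of these, in the section that governs the randomization phase, ends therapy at relapse. The capsules may be ibrutinib.

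The situation is foreseeable. Reintroduction is offered, not required. Section 8.4 makes it depend on Medical Monitor approval and on entry criteria such as creatinine clearance of at least 60 mL/min and no need for a strong CYP3A inhibitor. It also lets the start be delayed until treatment is indicated by IWCLL criteria. Section 9.2 deals with subjects who refuse reintroduction after confirmed progression, but says nothing about refusal after MRD-positive relapse alone.

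What is at stake is mainly patient management. Section 5.4.1.4 warns that holding single-agent ibrutinib for as little as a week can make disease transiently worse. Inconsistent handling between sites would also blur later progression-free survival (PFS), survival and safety summaries by arm.

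**Working it through.** **Step 1: the rules side by side, at confirmed MRD-positive relapse without progression.**

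| Place | Placebo | Ibrutinib |
|---|---|---|
| Protocol 8.2; SAP 1.1 | stop | stop |
| Protocol 5.3.2.1; synopsis | stop | continue |
| Protocol 5.5/9.2; 8.2.2 | not a listed stop | not a listed stop |

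The first two rows conflict on ibrutinib. The third conflicts with the first on both arms and with the second on placebo. The second row is evidently the intended rule. It is the only one written arm by arm, and 3.1.2 and the synopsis agree with it by letting a relapsing ibrutinib-arm subject stay on ibrutinib and add venetoclax.

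**Step 2: who is left without the code.** If reintroduction is planned, SAP 1.7.1 releases the code and the conflict resolves itself. The subjects left have confirmed MRD-positive relapse without progression and decline reintroduction, fail the 8.4 criteria, or defer with no plan.

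**Step 3: size.** Inputs from Protocol 10.3 and SAP 1.4: 150 enrolled, 40% confirmed MRD-negative, 1:1 allocation, 1-year disease-free rate 60% on placebo, a 30% improvement, about 80% power with 60 subjects.

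The plan's figure first. Reading the improvement as 30 percentage points (60% to 90%), power with unpooled variance is Φ(0.30 / √((0.60×0.40 + 0.90×0.10)/30) − 1.96) = Φ(0.30/0.105 − 1.96) = 81.6%; with pooled variance it is 78.0%. Both fit about 80%, so 90% is the planning rate for ibrutinib.

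- Randomized: 150 × 0.40 = 60, or 30 per arm.
- Expected year-one DFS events: ibrutinib 30 × 0.10 = 3 (binomial 95% range 0 to 7); placebo 30 × 0.40 = 12.
- Share of events on ibrutinib: 3/15 = 20%.

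SAP 1.5.1 reports confirmed MRD negativity in 11 of 14 early subjects. If that held for all 150 and all were randomized:

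- 150 × 11/14 = 117.9, or 58.9 per arm; ibrutinib events 58.9 × 0.10 = 5.9.
- Over the exact 95% interval for 11/14 (0.492 to 0.953): 36.9 to 71.5 per arm, so 3.7 to 7.2 events.

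These counts include progression and death. The documents do not give the share that is MRD-positive relapse without progression and without planned reintroduction. Any share from 0 to 1 gives 0 to 3 expected subjects at planning rates. As an illustration only, 25% to 50% gives 0.75 to 1.5, or 1.5 to 2.9 at the 11/14 rate.

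**Step 4: the primary test.** SAP Table 2 counts MRD-positive relapse as a DFS event, so nothing done afterwards changes the event or its date.

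**The case against.** The strongest reply is that treating until relapse in 8.2 and SAP 1.1 simply marks the end of the blinded assignment, and that what follows is stated many times. Section 3.1.2, the synopsis, 5.3.2.2 and Appendix A footnote t all send relapsing ibrutinib-arm subjects to added venetoclax. SAP 1.1 itself goes on to say that they may continue ibrutinib. The protocol governs sites, and it already permits unblinding at confirmed relapse. A subject who defers under 8.4 can still be said to plan reintroduction. Figure 2, the Section 3.2 schema and the Minimizing Bias Document, none of them visible here, may settle the rest.

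Much of this stands, and it narrows the problem. It does not remove it. Continuing ibrutinib is described in connection with adding venetoclax, so the subject who does not add it is not clearly covered. SAP 1.7.1 is stricter than the protocol on access to the code. No supporting document would correct the text of 8.2 or SAP 1.1.

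Two stronger readings should be resisted:

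- A reader might infer that 5.5/9.2 and 8.2.2 also stop only placebo. They do not: they name MRD-positive relapse for neither arm, and so miss the placebo stop as well.
- A reader might take another sentence in 8.2, that "the subject should continue to receive study medication, at the discretion of the Investigator, until MRD-positive relapse or disease progression is confirmed respectively", as an order to withdraw ibrutinib once relapse is confirmed. It applies while MRD is rising or progression is suspected, and mainly guards against stopping before confirmation.

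**Conclusion.** The inconsistency is real and sits in operative text. The documents contain the intended rule, in 5.3.2.1 and the synopsis; 8.2 and SAP 1.1 misstate it, and 9.2 omits its placebo half. The risk is that a site without the code withdraws active ibrutinib from a subject with MRD-positive relapse and no progression. It is a small risk: some unknown part of about 3 ibrutinib-arm events in year one at planning rates, or about 6 if the early MRD-negativity rate held. More events would follow in later years. The size rests on the planning rates and, for the larger figure, on extrapolating from 14 subjects.

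A reader might infer bias in the primary analysis. The documents do not support that, since relapse closes DFS follow-up as an event. Nor do they support saying that the trial offers relapsing ibrutinib subjects no way to stay on drug. It does, and the gap concerns those who take up no reintroduction. This is worth correcting because it touches patient care and costs little.

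**What to change.** 1. **Protocol 8.2 and SAP 1.1:** adopt the 5.3.2.1 rule. At confirmed MRD-positive relapse placebo stops; ibrutinib continues, with or without venetoclax, until progression (after reintroduction where that applies), toxicity or another reason in 9.2.
2. **Protocol 9.2:** add confirmed MRD-positive relapse, placebo arm only, since 5.5 treats this list as complete.
3. **SAP 1.7.1:** allow unblinding at confirmed MRD-positive relapse whether or not reintroduction is planned, keeping the independent clinician's check and the IRT approval. State that blinded capsules are not stopped for MRD-positive relapse until the code is broken. Permission alone is not enough, because a site that does not ask for the code cannot apply rule 1.
4. **Editorial, Protocol 8.4:** add MRD-negative subjects randomized to ibrutinib to the Venetoclax list, to match 3.1.2 and Appendix A footnote t.

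The cost is wording plus a few extra code breaks. These come after the DFS event, so the primary test is untouched. Later investigator-assessed progression, which feeds PFS, would be unblinded in those subjects, as it already is for those unblinded to reintroduce. A placebo subject whose code is not requested would stay on inert capsules a little longer.
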